**AIMS**

Aim 1-: To determine the effect of nutraceutical supplement (Thompson's Super Bioflavonoid Complex®) as natural DPP-4 inhibitor on glycaemic control in prediabetes and type 2 diabetes mellitus (T2DM).

**HYPOTHESES**

Hypothesis 1-: Thompson's Super Bioflavonoid Complex® (*two capsules per day for 12 weeks*) will significantly reduce DPP-4 activity in prediabetes and type 2 diabetes, increasing incretin hormone levels, and improving the blood glucose response to a glucose challenge and reduce the degree of oxidative stress.

This study will investigate the potential of commercially available nutraceutical supplements (Thompson's Super Bioflavonoid Complex®, 500 mg (Citrus Bioflavonoid capsules, two capsules/day) to reduce blood glucose levels in patients with prediabetes and T2DM. The action of these supplements is thought to be similar to the dipeptidyl peptidase-4 (DPP-4) inhibitor group, also known as gliptins, which are second line anti-diabetic drugs after metformin and sulfonylureas. The gliptins block the action of DPP-4, an enzyme which inhibits a group of gastrointestinal hormones called incretins [1]. Incretins help stimulate the production of insulin when it is needed (e.g. post meal) and reduce the production of glucagon by the liver when it is not needed (e.g. during digestion). By protecting incretins, DPP-4 inhibitors help regulate blood glucose levels. Studies have shown that gliptins possess side effects which include (but not limited to) flu-like illness, joints pain, and pancreatitis [1]. Naturally derived DPP-4 inhibitors may offer an alternative to prescription based gliptins, or as "add on" therapy to first line products and decrease the risk of developing diabetic complications. This will also reduce the financial burden (total annual cost of the antidiabetic medicine is around AU\$193.8 million) [2].

**BACKGROUND**

Since T2DM is a progressive condition, most patients will eventually require further treatment with more than one anti-diabetic drug to maintain their glycaemic goals [3]. Clinical evidence from the A Diabetes Outcome Progression Trial (ADOPT) and the United Kingdom Prospective Diabetes Study (UKPDS) shows that many T2DM patients on monotherapy will fail to maintain glycaemic control after just a few years, or even sooner, depending on disease duration prior to diagnosis and treatment adherence [3]. Given the failure of current treatments to provide long-term glycaemic control in a substantial proportion of patients, there is strong evidence for the need for new, better optimized treatment options [4], including evidenced based nutraceuticals. It should be noted that drugs of natural origin have a good track record in T2DM drug development; a recent review of all drugs approved worldwide since 1981 found 15 of 19 antidiabetic drugs (excluding biologicals such as insulin) have been either natural products or derived from natural product pharmacophores [5]. The chemically known anti-diabetics "dipeptidyl peptidase-IV (DPP-4) Inhibitors", also known as gliptins, control blood glucose levels via inhibiting the DPP-4 enzyme action on incretin hormones, and hence improve insulin secretion [6]. Recent studies have explored

the naturally related active compounds which possess DPP-4 Inhibitor activity. These can be generally divided into two main types: phytosterols and bioflavonoids [7].

Bioflavonoids are classified as organic polyphenolic compounds, which are found in various plant-based foods in different concentrations, like berries and citrus fruits. Citrus bioflavonoids can be specified as plant pigments available in various sources such as oranges, lemons and grapefruits. They have the capability of enhancing the absorption levels as well as the utilisation of vitamin C [8]. Thompson's Super Bioflavonoid Complex® contains citrus bioflavonoid extract-500 mg, ascorbic acid-390 mg, rutin-100 mg, and sodium ascorbate-125.3 mg (equiv 110 mg Ascorbic Acid). Lemon bioflavonoid is the source of eriocitrin [9], which possesses a lipid lowering activity as seen in animal models [9]. Orange bioflavonoid comprises hesperetin, hesperidin and naringenin [10]. These possess potent antioxidant activity as seen in previous studies [11]. Other *in-vivo* studies signified the impact of naringenin and hesperidin in suppressing macrophage infiltration [11], and reducing blood glucose levels [12]. The grapefruit bioflavonoid contains mainly naringenin, which is beneficial in reducing arterial stiffness in post-menopausal women [13], and helps improving hyperglycaemia [14]. A more recent study investigated the effects of diabetinol (nobiletin-49%, tangeretin-13%, including limonoids, tocotrienols and vitamin E) on glycaemic control in patients with impaired fasting glucose [15].

## METHODS

### Design

**Participants:** Fifty participants recently diagnosed with prediabetes and/or T2DM living in Hobart/Launceston regions will be recruited for this study. The study will be conducted in two clinical areas: 1- Medical Science Precinct, University of Tasmania (UTAS), Hobart. 2- School of Health Sciences, Newnham campus, Launceston. Potential participants will be identified by local media, flyers, local General Practices, as well as by the Diabetes clinic at the Royal Hobart Hospital and Launceston General Hospital. Participants will undergo the following:

1. Medical & lifestyle questionnaires (general health, diet & physical activity questionnaires).
2. Anthropometrics (body weight, height, waist & hip circumference).
3. Blood tests to measure blood glucose, HbA1c, serum lipids, insulin, & oxidative markers (8-hydroxy deoxy Guanosine (8-OHdG), and resistin).
4. DPP-4 activity in the blood before and after 12 weeks.
5. Glucose metabolism (2hr oral glucose tolerance test).
6. Haemodynamic measures (blood pressure, heart rate & ECG).
7. Urinary electrolytes & kidney function.

**Research design:** This is a randomized double-blinded placebo-controlled study. The total duration of the recruitment process is 12 weeks.

Participants will be randomly allocated into two study groups (25 participants in each study group): Study group (Group-1) include participants who use the nutraceutical supplement (Thompson's Super Bioflavonoid Complex®) for 12 weeks and continue on their current anti-diabetic treatment with no interruption. Control group (Group-2) include participants who use the placebo capsules for 12 weeks and continue on their current anti-diabetic treatment with no interruption.

The placebo capsules would contain the same excipients as the active capsules, but the active herbal extract would be replaced by excipients.

The excipients in the Thompson's Super Bioflavonoid Complex are microcrystalline cellulose (BP), calcium hydrogen phosphate dehydrate (USP), silica – colloidal anhydrous (BP), crospovidone (BP) and magnesium stearate (BP).

As per the instruction provided, the supplements will need to be stored below 30 °C in a dry place.

[figure not shown]

Figure 1: Overview of the study.

### Setting

The study will be conducted in clinical areas at: 1- Medical Science Precinct, University of Tasmania (UTAS), Hobart, and 2- The Clinical rooms at the School of Health Sciences, Newnham campus, Launceston.

### Participants

#### *Inclusion Criteria:-*

For all participants

1. Have been clinically diagnosed with prediabetes and/or early stage type 2 diabetes (on diet and lifestyle intervention or metformin only treatment).
2. Aged between 25 – 75 years.
3. Lean, overweight or obese (BMI 19-35 kg/m^2).
4. Have normal or controlled blood pressure (Seated brachial blood pressure <140/90 mmHg).
5. Have given signed informed consent to participate in the study.
6. Willing to take nutraceutical supplement (Thompson's Super Bioflavonoid Complex®), for 12 weeks.

*Exclusion Criteria:-*

For all participants

1. Age <25 yrs or >75 yrs
2. Morbidly obese with a BMI  $\geq 35$  kg/m^2
3. Not on diet and lifestyle or metformin only treatment for their diabetes (e.g. insulin injections, sulphonylureas, GLP-1 receptor agonists).
4. History of myocardial infarction or stroke
5. History of malignancy within past 5 years (except for non-melanoma skin cancers)
6. Identification of any medical condition requiring immediate therapeutic intervention
7. Uncontrolled hypertension (resting brachial blood pressure  $\geq 160/100$  mmHg)
8. History of severe liver disease
9. History of drug or alcohol abuse
10. Elective major surgery during the course of the study
11. Pregnancy/lactation
12. Currently consuming nutraceutical supplements (especially vitamin C and D)
13. Participation or intention to participate in another clinical research study during the study period.
14. Not willing to take nutraceutical supplements (Thompson's Super Bioflavonoid Complex®), for 12 weeks.
15. Participants with impaired renal function.

Participants will be invited from Hobart/Launceston regions who are able to come to the clinical areas at Medical Science Precinct/School of Health Sciences, UTAS. Venous blood samples & urine samples will be collected at the start of the study. Thompson's Super Bioflavonoid Complex® supplement will be provided to the participants for 12 weeks, and samples will be collected at the end of the study to compare the results of the selected markers aiming to identify the metabolic response to these nutraceutical supplements.

Biomarkers of metabolic response included in this study are 8-hydroxy deoxyguanosine (8-OHdG) (oxidative DNA damage), total lipid peroxidation (lipid peroxidation), interleukin-6 (Inflammatory response) and resistin (adipocytokine response).

*Sample size Justification*

Our previous data shows that we had statistical significant changes in the levels of 8-OHdG and antioxidants using 40 T2DM patients [16]. Based on these data and assuming 20-25% withdrawal rate from the study, for a two sample test (t-test) with a Type I error of 5% ( $\alpha = 0.05$ ) and 80% power, we will require 50 participants in each group.

*Recruitment*

Potential participants will be identified by radio, flyers, local General Practices, and by the Diabetes clinic at the Royal Hobart Hospital/Launceston General Hospital. Potential participants may be contacted using the National Diabetes Services Scheme (NDSS) through Diabetes Tasmania. Participants from previous studies may be contacted if they have given consent to be contacted for future studies.

Participants who meet the inclusion/exclusion criteria will receive the participant information sheet/consent form inviting them to take part. Contact details of the study coordinator will be given, so that participants can raise any queries or concerns that they have and inform of their interest in participating in the study.

Participants from previous studies will be contacted via telephone, email or mail regarding the study and will be given the opportunity to contact the study coordinator if they are interested. Participants responding to online, print media and radio advertisements will be invited to contact the study coordinator by telephone or email. Initial screening will be based on a health history questionnaire and questions prior to attendance to rule out exclusion criteria.

[figure not shown]

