## TASMANIAN SCIENTIFIC RESEARCH ADVISORY COMMITTEE

Ascorbic Acid (Vitamin C) & Sodium ascorbate (125.3mg) equiv. Ascorbic Acid (Vitamin C)110mg)	390 mg + 110= 500mg
Rutin	100 mg

Participants will be asked to complete a logbook to record the day and time they take the capsules. Participants will be asked not to change any other lifestyle factors (e.g. diet or level of physical activity). During the last week of the Thompson's Super Bioflavonoid Complex® supplementation/Placebo study, they will be asked to repeat the food questionnaire and the physical activity questionnaire. This will be filled out at home and brought to the clinic on visit 2.

*Pharmacokinetics/pharmacodynamic study:*

During visit 1, and after the first dose of Thompson's Super Bioflavonoid Complex® supplementation/ Placebo, additional blood and urine samples will be collected following the first dose of the supplement to measure the pharmacokinetics/pharmacodynamics characteristics of a single dose administration of the citrus bioflavonoid in human body. A series of blood and urine samples will be collected at times (0, 1, 2, 4, 8 and 24) hours. Participants will be able to move around and stay within the clinical area for the first 4 hours, and they can leave and come back for the 8 hrs and 24 hrs time of collection.

Commented [HA1]: All, please amend this as you think more appropriate.

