### Data analysis

Data analysis will be done using SPSS program (IBM SPSS Statistics version 22), and Microsoft Excel 2010. All values will be expressed as mean  $\pm$  SEM. Statistical analyses will be performed using a one-way ANOVA followed by unpaired Student's t test and paired students t-test (individual results before and after the course of supplements)-LSD- (Least significant difference) (non-parametric, with two-tailed) will be used for non-parametric results (to compare patients versus control results). Results will be considered significant at P equal or < than 0.05.

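### Eligibility sets no period of unchanged background treatment before Visit 1, so newly treated participants add variance to the 12-week change and make the before/after test still harder to attribute to the supplement

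*Protocol*

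**What the plan says.** The Design section describes the target population as "Fifty participants recently diagnosed with prediabetes and/or T2DM" and does not define how recent the diagnosis must be. Inclusion item 1 admits people with prediabetes or early type 2 diabetes who are "on diet and lifestyle intervention or metformin only treatment". Exclusion item 3 removes those on other glucose-lowering treatment. Both items concern the kind of treatment. Neither gives a minimum time since it began or a period of unchanged dose, and the text describes no run-in.

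During the 12 weeks both arms are to "continue on their current anti-diabetic treatment with no interruption". The supplementation part of Visit 1 adds: "Participants will be asked not to change any other lifestyle factors (e.g. diet or level of physical activity".

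On design and analysis, the protocol states "This is a randomized double-blinded placebo-controlled study", with "25 participants in each study group". The Data analysis section plans "one-way ANOVA followed by unpaired Student's t test" and also a "paired students t-test (individual results before and after the course of supplements". The eligibility visit lists anthropometrics, questionnaires and blood pressure. Glycaemic blood sampling starts at Visit 1, so there is one glycaemic baseline.

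**The concern.** People with a recent diagnosis are the ones most likely to have just begun metformin or a lifestyle programme. Keeping that treatment constant after Visit 1 does not stop it from still taking effect. Their glucose, HbA1c, lipids and insulin sensitivity may then move over the 12 weeks whatever capsule they take, while those of long-settled participants do not. With a single baseline, the data cannot show who was already improving.

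Two things are at stake:

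- **Precision of the between-arm comparison.** A mixture of settled and settling participants has a wider spread of change, and the trial is small.
- **Reading of the paired test.** Any average improvement from background treatment appears in the active arm's before/after change, where it could be taken for a supplement effect.

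**Working it through.** **No protocol figure to reproduce.** The protocol gives no SD of change, no share of recent starters and no size of settling-in. Its sample-size paragraph gives no effect size or SD either. The calculation is therefore an illustration on declared assumptions.

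**Inputs**
- From the protocol: n = 25 per arm (Design section), two-sided 5% level. The sample-size paragraph says 50 per group. That conflict is a separate matter, and the variance ratios below do not depend on n.
- Assumed: share of recent starters p = 0.3; their HbA1c fall over 12 weeks, in either arm, d = 0.5 or 1.0 points; SD of change among the rest s = 0.5 or 0.7 points.

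**Step 1: bias of the between-arm difference.** Settling-in shifts the expected change by p × d in both arms, so the expected difference is p·d − p·d = 0. In a simulation with no supplement effect (20% to 50% recent starters, settling-in of 0.5 to 1.5 SD, 20 or 25 per arm), the unpaired test was significant in about 5% of trials and the mean bias was about 0.

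**Step 2: variance of the change.** Variance = s² + p(1−p)d², with p(1−p) = 0.21. The standard error of the arm difference is √(2 × variance/25).

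| s | d | Variance | Ratio to s² | SE without → with settling-in |
|---|---|---|---|---|
| 0.7 | 0.5 | 0.49 + 0.0525 = 0.5425 | 1.11 | 0.198 → 0.208 |
| 0.5 | 0.5 | 0.25 + 0.0525 = 0.3025 | 1.21 | 0.141 → 0.156 |
| 0.7 | 1.0 | 0.49 + 0.21 = 0.70 | 1.43 | 0.198 → 0.237 |
| 0.5 | 1.0 | 0.25 + 0.21 = 0.46 | 1.84 | 0.141 → 0.192 |

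Variance rises by 11% to 84%, and the standard error by 5% to 36%. By the normal approximation, a comparison with 80% power in settled participants would have Φ(2.80/√ratio − 1.96), which is 0.76 at a ratio of 1.11 and 0.54 at 1.84.

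**Step 3: chance imbalance is the same quantity.** Uneven numbers of recent starters contribute d√(2p(1−p)/25) = 0.065 (d = 0.5) or 0.130 (d = 1.0) to the standard error. This equals √(SE_with² − SE_without²) from Step 2. It is the added variance in another form.

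**Step 4: the paired test with no supplement effect.** The mean change is p·d = 0.15 or 0.30. The noncentrality is p·d/√(variance/25), which runs from 0.15/(0.7365/5) = 1.02 to 0.30/(0.678/5) = 2.21. From the noncentral t distribution with 24 degrees of freedom, the test is significant with probability 0.165 to 0.565 instead of 0.05.

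**Step 5: what exclusion would cost.** At p = 0.3, about 0.3 × 50 = 15 people would be delayed or excluded. If they are not replaced, the variance of the arm difference is multiplied by 1/0.7 = 1.43. That equals or exceeds the settling-in penalty in three of the four rows above, so unreplaced exclusion gains precision only in the last row.

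**The case against.** The strongest reply is that placebo control and randomisation already deal with this. Settling-in falls on both arms and cancels on average. That stands. A reader might infer from the missing criterion that the active-versus-placebo difference confuses background response with supplement effect. The design does not support that reading, and Step 1 confirms it. Nor is chance imbalance a second harm beyond added variance: the unpaired test already carries it in its standard error (Step 3).

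A reader might also see a contradiction between enrolling people on a lifestyle programme and telling them not to change their lifestyle. The instruction concerns other factors ("Participants will be asked not to change any other lifestyle factors (e.g. diet or level of physical activity"), and current treatment is to continue. Someone on a diet programme complies by staying on it.

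It is also fair to say that the figures in Step 4 belong mainly to the paired test itself. A before/after change in one arm includes placebo response and regression to the mean even when every participant is stable. An eligibility line would lessen the problem without curing it.

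The magnitude is assumed. With 10% recent starters the paired-test probability is 6% to 13%. Inclusion item 1 itself does not require a recent diagnosis, and recruitment also draws on a diabetes register and earlier studies, whose members need not be newly treated. The questionnaires and figures are not shown and may already record a start date or describe screening more fully.

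What remains is that the eligibility list, which is shown, has no stability requirement, and that continuing treatment unchanged from Visit 1 does not supply one.

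**Conclusion.** The point holds as a matter of precision and interpretation. The criteria restrict the type of background treatment but not how long it has been unchanged, in a trial aimed at recently diagnosed people. The randomised comparison remains unbiased. The variance of the 12-week HbA1c change would rise by 11% to 84% if 30% are recent starters with a 0.5 to 1.0 point fall and the SD of change is otherwise 0.5 to 0.7. None of these inputs comes from the protocol, and a smaller share of recent starters would give a smaller penalty. The direction does not depend on the inputs: any mixture of settled and settling participants widens the spread.

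The paired before/after test cannot be attributed to the supplement in any case, and settling-in worsens this. This is a matter for the protocol, because a later analysis plan cannot change who was enrolled and can adjust for time since treatment start only if that date is collected.

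**What to change.** Add to inclusion item 1 that background treatment has been unchanged for a stated period before Visit 1. The investigators should set the length. Define the recently diagnosed target in the Design section so that it agrees with this.

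If the 12-week recruitment period cannot bear the exclusions, keep eligibility as it is, record the treatment start date at the screening already planned, and stratify or adjust the between-arm comparison for time since start. Step 5 favours this route if excluded participants would not be replaced.

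In either case, state that the conclusion rests on the between-arm difference and that the paired before/after test is descriptive.

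Cost: for the first route, one line in the criteria and one screening question, with some of the newest diagnoses delayed or ineligible (about 15 of 50 if 30% are recent starters). For the second, one screening question and one extra covariate or stratification factor.

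### The protocol randomises 25 per group but states that 80% power requires 50 per group; the two figures conflict, and no difference or SD is given to show which is right

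*Protocol*

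**What the plan says.** Under Methods, Design, the protocol gives the enrolment twice, and the two statements agree. The total is "Fifty participants recently diagnosed with prediabetes and/or T2DM living in Hobart/Launceston regions will be recruited for this study". The allocation is "Participants will be randomly allocated into two study groups (25 participants in each study group".

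Under Sample size Justification, the planned test is "for a two sample test (t-test"), at a type I error of 5%, "assuming 20-25% withdrawal rate from the study", and the result is "80% power, we will require 50 participants in each group". The only empirical basis offered is an earlier study that found "statistical significant changes in the levels of 8-OHdG and antioxidants using 40 T2DM patients". The section names no difference, SD or endpoint for the t-test, and does not say whether the test is one- or two-sided.

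**The concern.** Two groups of 50 make 100 participants; the Design section plans 50. Both statements are complete sentences in the body text, so this is not a gap left by the PDF conversion, and the missing figures could not remove a conflict between two sentences. Nor is it a detail that a protocol normally leaves to the SAP: the protocol states the enrolment and its justification itself, and they disagree.

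At stake is whether 50 or 100 people are to be randomised, and what the trial can detect. A reader who takes the 80% power at face value will attach it to a design half the size for which it was stated.

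**Working it through.** **Inputs.** From Sample size Justification: two-sample t-test, alpha 0.05, power 80%, withdrawal 20-25%, requirement 50 per group. From Design: 25 per group. Assumed: a two-sided test. The sample size section is silent on this; Data analysis mentions two tails, but only in a clause on non-parametric results ("non-parametric, with two-tailed"). The one-sided result is therefore shown as well.

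**1. Can the plan's 50 per group be reproduced?** No. The formula n per group = 2(z_alpha + z_beta)²/d² needs the standardised difference d (difference divided by SD), which the protocol does not give. One can only solve backwards for the d that makes 50 per group sufficient. Noncentral t, two-sided, 80% power:

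| Analysed per group | Implied d |
|---|---|
| 50 (no withdrawal) | 0.566 |
| 40 (20% withdrawal: 50 × 0.80) | 0.634 |
| 37.5 (25% withdrawal: 50 × 0.75) | 0.656 |

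**2. Power with 25 per group, if 50 per group is right.** With the same d and the same withdrawal fraction, the number analysed halves. Under the normal approximation d and the withdrawal fraction then cancel:

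power = Φ((z_alpha + z_beta)/√2 − z_alpha)

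- Two-sided: Φ((1.960 + 0.842)/1.414 − 1.960) = Φ(0.021) = 50.8%.
- One-sided: Φ((1.645 + 0.842)/1.414 − 1.645) = Φ(0.113) = 54.5%.

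The two-sided noncentral t gives 50.0%, 49.8% and 49.7% at 0, 20 and 25% withdrawal (25, 20 and 18.75 analysed per group). One-sided it gives about 54%.

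**3. The most favourable variant.** Suppose that 50 per group already allows for withdrawal, but nobody withdraws from the 25 per group.

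- 20% allowed for: Φ(2.802 × √(25/40) − 1.960) = Φ(0.255) = 60.1%; 59.4% by noncentral t at d = 0.634.
- 25% allowed for: Φ(2.802 × √(25/37.5) − 1.960) = Φ(0.328) = 62.8%; 62.2% by noncentral t at d = 0.656.

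**4. What 25 per group can detect with 80% power** (two-sided noncentral t):

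| Completers per group | Detectable difference |
|---|---|
| 25 (no withdrawal) | 0.81 SD |
| 20 (25 × 0.80) | 0.91 SD |
| 18.75 (25 × 0.75) | 0.94 SD |

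**5. The other reading.** The earlier study had 40 patients. If 40 were taken as a total and inflated for 20% withdrawal, 40/0.80 = 50 in total, and 20/0.80 = 25 per group, which matches the Design section. On that reading the words placing 50 in each group are a slip. The same arithmetic fits 40 completers per group equally well (40/0.80 = 50 per group), so it does not settle which was meant.

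**The case against.** The strongest objection is to the power loss, not to the contradiction. A reader might infer that the trial has about 50% power. The documents do not support that as a plain fact: with no difference or SD stated, the true power of the design is unknown, and the 50% holds only if 50 per group is the real requirement. The slip reading in step 5 is plausible, and under it no shortfall follows. This objection stands, and the power figures here are conditional for that reason.

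It does not remove the error. If a total of 50 was meant, the only stated requirement in the protocol is wrong, and the 80% power claim rests on no stated effect size. Statistical significance in an earlier study of 40 patients is not by itself a power calculation for a two-group comparison.

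A reader might also conclude that the withdrawal inflation was done wrongly, because 40/0.75 = 53.3 exceeds 50. That would criticise a calculation the protocol does not show; 40 × 1.25 = 50 would reproduce the figure too. The documents do not say how the 50 was obtained, so no error in the inflation can be established.

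**Conclusion.** The contradiction is certain: 50 participants in total under Design against 100 under Sample size Justification, with nothing in the protocol to reconcile them. Which figure is right cannot be decided from the document.

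Conditional on 50 per group being the true requirement, the randomised design has about 50% power instead of 80%, assuming a two-sided test, the same difference and the same withdrawal rate. It is about 54% if one-sided. It is about 59% two-sided if 50 per group allows for 20% withdrawal and all 25 per group complete, or about 62% if it allows for 25%. None of these comes near 80%.

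Conditional on a total of 50 being meant, no loss of power follows, but the stated requirement is wrong and the 80% claim is unsupported. On either reading the sample size statement is wrong as written and has to be corrected.

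**What to change.** Make one figure govern in both sections.

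- **If 50 in total is the real size:** delete the requirement of 50 per group and restate the justification along these lines: 25 randomised per group, about 19-20 completers after 20-25% withdrawal, give 80% power (two-sided alpha 0.05) for a between-group difference of about 0.91-0.94 SD. Add the difference and SD for the endpoint on which the calculation is based, so that a reader can judge whether an effect of that size is realistic. The cost is a wording amendment and a less favourable power statement; no extra participants are needed.
- **If 100 was intended:** correct the total and the group sizes under Design. This doubles planned enrolment, from 50 to 100, and so is not a wording change. The difference and SD behind the 50 per group should still be stated.

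In either case, state whether the test is one- or two-sided.
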